## 8.4 Covariates and Subgroups

(ICH E3; 9.7.1, 11.4.2.1. ICH E9; 5.7)

In all formal hypothesis testing, the models will be adjusted for the following covariates:

1. ANCA type (anti-PR3 or anti-MPO)
2. Relapse severity (severe or non-severe)
3. Selected prednisone induction regimen (1A or 1B)

the same stratifying variables used for randomisation.

## 8.5 Missing Data

(ICH E3; 9.7.1, 11.4.2.2. ICH E9; 5.3. EMA Guideline on Missing Data in Confirmatory Clinical Trials)

The sample size of non-missing values will be reported for summary tables. It is expected that the incidence of missing data will be low. Missing data will be assumed to be missing at random. In practice, missing values will be ignored for calculation of summary statistics. The number of non-missing values will be reported and used instead of the population or subgroup size as a denominator as needed. The overall size of the population, including missing values will be reported within the title of the table or figure to convey the amount of missing data.

Due to logistic reasons, the PROMIS questionnaire was not administered to the full study population. The number of sites and patients not taking part will be noted.

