### 9.6.2 Secondary endpoints

1. Proportion of patients who maintain remission at 24 and 48 months
2. Time to a major or second minor relapse
3. Cumulative accrual of damage as measured by the combined damage assessment score (CDA)
4. Health-related quality of life as measured using SF-36
5. Cumulative GC exposure
6. Severe adverse event rate
7. Infection (treated with intravenous or oral antibiotics) rates

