### 5.2.2 Secondary endpoints

1. Proportion of patients who maintain remission at 24 and 48 months.
2. Time to a major or second minor relapse.
3. Cumulative accrual of damage as measured by the combined damage assessment score (CDA).
4. Health-related quality of life as measured using SF-36.
5. Cumulative GC exposure.
6. Severe adverse event rate.
7. Infection (treated with intravenous or oral antibiotics) rates.

 Time measured from enrolment.

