### 6.4 Study Schedule

(ICH E3; 9.5.1. ICH E9; 2.2.2)

Table 2 illustrate the schedule of events for the entire trial. The induction phase of the trial comprises the first 4 months from enrolment. At month 4 patients who have achieved remission are randomised to either maintenance therapy with rituximab or azathioprine. The maintenance phase of the trial, comprising 20

months of treatment and a 12–24 months follow up phase, commences at month 4 from enrolment.

Completed Case Report Forms (CRFs) are expected to be returned to the trial coordinating centre within 2 weeks of evaluation and the Data Manager routinely queries sites for missing/delayed forms.

Important notes regarding the schedule of events:

- The Screening and Month 0 visits must take place within 2 weeks of each other.
- The Treatment Form at Month 0 visit is completed by the PI at weeks 1, 2, 3 and 4 for rituximab infusion.
- Laboratory tests results are permitted to be within  $\pm 2$  weeks of the date of the study evaluation.
- Unscheduled assessments are performed at the time of relapse or study termination/withdrawal. Unscheduled assessment are retained for safety reviewing and not incorporated in the summary statistics of the scheduled visits.
- Biomarker research samples are taken prior to rituximab infusion.

Table 2: Time and events schedule

	Screening	Month 0	Month 1.5	Month 3	Month 4 (R)	Month 8	Month 12	Month 16	Month 20	Month 24	Month 27	Month 30	Month 36	Month 42	Month 48	Unscheduled Visit
Forms																
Enrolment	X															
Demographics	X															
Weight	X				X											
Height	X															
Urinary HCG		X														
Baseline Medical History	X															
Comorbidities	X															
Concomitant Medication	X	X	X	X	X											X
Follow Up		X	X	X	X	X	X	X	X	X	X	X	X	X	X	X
Treatment		X			X	X	X	X	X							
BVAS/WG		X	X	X	X	X	X	X	X	X	X	X	X	X	X	X
CDA		X			X		X			X			X	X	X	X
SF-36, EQ5D		X			X		X			X			X	X	X	X
PROMIS questionnaires	X	X	X	X	X	X	X	X	X	X	X	X	X	X	X	X
Adverse event review		X	X	X	X											

	Screening	Month 0	Month 1.5	Month 3	Month 4 (R)	Month 8	Month 12	Month 16	Month 20	Month 24	Month 27	Month 30	Month 36	Month 42	Month 48	Unscheduled Visit
Clinical Labs																
FBC/CBC	X	X	X	X	X	X	X	X	X	X	X	X	X	X	X	X
ESR	X	X	X	X	X	X	X	X	X	X	X	X	X	X	X	X
Chemistry (electrolytes, creatinine, LFTs)	X	X	X	X	X	X	X	X	X	X	X	X	X	X	X	X
CRP	X	X	X	X	X	X	X	X	X	X	X	X	X	X	X	X
ANCA	X	X	X	X	X	X	X	X	X	X	X	X	X	X	X	X

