### 4. Disease related assessment (CDA)

- **Total CDA score (integer)** – Accrual of damage as measured by the combined damage assessment (CDA) score. Each persistent or new occurrence of damage is recorded as "Yes" and given a score of 1. The cumulative accrual of damage is obtained by summing across the

different types of damage to get an overall score (max score = 64). The variable will be reported both as categorical and continuous.

- **Change in total CDA score between month 4 and month 12 (integer)** – difference in Total CDA score between month 4 (randomisation) and month 12, calculated for complete–case records only. The variable will be reported both as categorical and continuous.
- **Change in total CDA score between month 4 and month 24 (integer)** – difference in Total CDA score between month 4 (randomisation) and month 24, calculated for complete–case records only. The variable will be reported both as categorical and continuous.
- **Change in total CDA score between month 4 and month 36 (integer)** – difference in Total CDA score between month 4 (randomisation) and month 36, calculated for complete–case records only. The variable will be reported both as categorical and continuous.
- **Change in total CDA score between month 4 and month 48 (integer)** – difference in Total CDA score between month 4 (randomisation) and month 48, calculated for complete–case records only. The variable will be reported both as categorical and continuous.
- **Change in total CDA score between month 24 and month 36 (integer)** – difference in Total CDA score between month 24 (end of maintenance treatment) and month 36, calculated for complete–case records only. The variable will be reported both as categorical and continuous.
- **Change in total CDA score between month 24 and month 48 (integer)** – difference in Total CDA score between month 24 (end of maintenance treatment) and month 48, calculated for complete–case records only. The variable will be reported both as categorical and continuous.

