## 12 Quality of Life Analysis

Health-related quality of life and patient-reported outcomes will be assessed using questionnaires. Exploratory analyses of Quality of Life data outcomes as planned in the protocol are to be carried out by the Cambridge team. Details are outside the scope of this SAP.

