## 12.2 SF-36 questionnaire

The 36-Item Short Form Health Survey (SF-36) is a set of generic, coherent, and easily administered quality-of-life measures.

The answers to each question will be reported at Month 4, 12, 24, 36, 42 and 48 visit, using the full analysis population. The SF-36 questionnaire will be scored according to the scoring method of the RAND 36-Item Health Survey 1.0^29. All 36 individual items of the questionnaire, as well as the total score of the following domains, will be summarised in accordance with section 9:

1. Physical Functioning (PF)
2. Bodily pain (BP)
3. Role limitations due to physical health (RP)
4. Role limitations due to emotional problems (RE)
5. Energy/fatigue (EV)
6. Emotional well-being (MH)
7. Social functioning (SF)
8. General health (GH)
9. Change in Health (CH)

Additionally, two distinct, higher order summary scores will be derived from the above domains:

1. Physical Component Summary (PCS)
2. Mental Component Summary (MCS)

calculated using the subscale scoring coefficients (Table 11) and reference populations mean and standard deviation (PCS: 82.261 and 20.867; MCS: 63.7796 and 19.582) employed in PEXIVAS study.

---

 [https://www.rand.org/health/surveys\\_tools/mos/36-item-short-form/scoring.html](https://www.rand.org/health/surveys_tools/mos/36-item-short-form/scoring.html)

 The scoring procedure is explained in detail in [13, 14].

Table 11: factor score coefficients for PCS and MCS (14)

Subscale	PCS coefficients	MCS coefficients
Physical Functioning (PF)	0.418	-0.213
Role limitations due to physical health (RP)	0.334	-0.087
Bodily pain (BP)	0.366	-0.125
General health (GH)	0.222	0.036
Energy/fatigue (EV)	-0.017	0.286
Social functioning (SF)	-0.083	0.201
Role limitations due to emotional problems (RE)	-0.179	0.394
Emotional well-being (MH)	-0.200	0.444

Formulas to calculate the PCS and MCS scores:

- For the PCS:  
 $AGPHYSICO = (PF * 0.456) + (RP * 0.362) + (BP * 0.367) + (GH * 0.199) + (EV * -0.050) + (SF * -0.028) + (RE * -0.110) + (MH * -0.256)$   
 $PCS = ((AGPHYSICO - 82.261) / 20.867) * 10 + 50$
- For the MSC: :  $AGMENTCO = (PF * -0.227) + (RP * -0.102) + (BP * -0.130) + (GH * 0.036) + (EV * 0.278) + (SF * 0.272) + (RE * 0.329) + (MH * 0.460)$   
and then  $PCS = ((AGMENTCO - 63.7796) / 19.582) * 10 + 50$

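### Within this SAP, CDA damage and SF-36, both secondary endpoints, get only unadjusted observed-case summaries by arm, with no between-arm estimate or confidence interval

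*SAP*

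**What the plan says.** Protocol 9.6.2 and SAP 5.2.2 both list CDA damage accrual (item 3) and "Health-related quality of life as measured using SF-36" (item 4) as secondary endpoints. SAP 5.2 says that the endpoints to be assessed are described in sections 9 to 12. Those sections provide the following.

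- **CDA** (SAP 9.2 item 4 and 9.8): the total score at each visit, the change from month 4 to months 12, 24, 36 and 48, and the change from month 24 to months 36 and 48. Each change is "calculated for complete–case records only".
- **SF-36** (SAP 12.2): the individual items, "as well as the total score of the following domains, will be summarised in accordance with section 9", plus the derived PCS and MCS. Section 9 means n, mean, SD, median and range per arm.
- **Further quality-of-life analysis** (SAP 12): called exploratory and assigned to the Cambridge team. "Details are outside the scope of this SAP".
- **Missing data** (SAP 8.5): "Missing data will be assumed to be missing at random. In practice, missing values will be ignored for calculation of summary statistics". The same section says "It is expected that the incidence of missing data will be low".
- **Unscheduled assessments** at relapse or withdrawal (SAP 6.4): "not incorporated in the summary statistics of the scheduled visits".
- **Models**: SAP 10.2 models two time-to-relapse outcomes only. One of them, time to major relapse, was not in the protocol. The covariates in SAP 8.4 are the three stratification factors, and they apply to formal hypothesis tests.

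**The concern.** Nothing in this SAP turns CDA or SF-36 into an estimate of the treatment effect. An outcome added after the protocol gets a Cox model, while two protocol-listed secondary endpoints get tables and plots. SF-36 is secondary in both documents, yet SAP 12 treats its analysis as exploratory along with EQ5D and PROMIS. In an open-label trial, an analysis method that is settled outside the SAP may be chosen with knowledge of the data.

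The stated assumption and the method also differ. Missing at random lets missingness depend on scores already observed. The plain mean of the observed values in an arm is then generally biased, because nothing in the calculation uses those earlier scores. Finally, the month 4 score is collected in all patients at the start of maintenance but is not a covariate for either endpoint. That gives up precision which costs nothing to obtain.

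**Working it through.** **The plan's own figure.** The documents give no SD, correlation, target difference or power for CDA or SF-36. The only sample-size figure is for relapse: 58 events for 90% power at a hazard ratio of 0.42, two-sided 5%. Schoenfeld's formula gives 4(1.960 + 1.282)² / (ln 0.42)² = 42.0 / 0.753, about 55.8, so 56 events. This agrees within 2 of the stated 58 but says nothing about these two endpoints.

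**Precision.** Let ρ be the within-arm correlation between the month 4 score and a later score, with equal variances at both times (assumptions). Relative to the raw follow-up mean, the variance of the arm difference is 1 for raw means, 2(1 − ρ) for change scores and 1 − ρ² with month 4 as a covariate. Adjusted against change is therefore (1 − ρ²) / [2(1 − ρ)] = (1 + ρ)/2.

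| ρ | adjusted / raw mean | adjusted / change score |
|---|---|---|
| 0.3 | 0.91 | 0.65 |
| 0.5 | 0.75 | 0.75 |
| 0.7 | 0.51 | 0.85 |
| 0.8 | 0.36 | 0.90 |
| 0.9 | 0.19 | 0.95 |

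At ρ of 0.5 to 0.7, the variance falls by 25–49% against raw means (the SF-36 summaries). That is worth 1/0.75 = 1.33 to 1/0.51 = 1.96 times the sample size. Against change scores (the CDA summaries) it falls by 15–25%, and by only 5% at ρ = 0.9.

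**Bias.** A simulation used 2,000,000 patients, SD 1, no true effect and equal correlation ρ of 0.5 to 0.8 between months 4, 12 and 24. In one arm, missingness at month 24 depended on the month 4 or month 12 score (log-odds 1 per SD). In the other it was random at the same rate. Absolute bias in SD units:

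| missing | raw observed means | complete-case change, missingness depends on month 4 |
|---|---|---|
| 5% | 0.02–0.04 | 0.01–0.02 |
| 10% | 0.04–0.07 | 0.02–0.05 |
| 20% | 0.09–0.14 | 0.04–0.09 |

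When missingness depended on month 12, the change score had almost no bias (0.001 SD or less). A likelihood estimate using months 4 and 12 had bias of about 0.001 SD or less throughout.

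**How much will be missing.** With 5% drop-out at 2 years (SAP 7), taken as exponential from month 4, the expected numbers are:

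- Month 24: 160 × 0.95^(20/24) = 153.
- Month 36: 160 × 0.95^(32/24) = 149.

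Recruitment lasts 24 months and the trial closes 36 months after the last enrolment. With uniform accrual (assumption), 75% of patients can reach month 42 and 50% can reach month 48:

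- Month 42: 120 × 0.95^(38/24) = 111.
- Month 48: 80 × 0.95^(44/24) = 73.

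The expectation of low missingness therefore cannot hold for those two visits. That loss follows entry date, so it mainly costs precision.

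**The case against.** Several stronger readings are tempting, and the documents do not support them.

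- **That the plan ignores the month 4 score.** For CDA it is the reference for the planned changes, and for SF-36 it is tabulated. It is only not used as a covariate.
- **That SF-36 has no prespecified analysis anywhere.** SAP 12 refers such analyses to work outside this SAP, which may have its own plan. What can be said is that none is specified here.
- **That patients who relapse miss visits, so the results will be biased.** No figure supports this. Protocol 10.6, 15.1.2 and 15.1.3 and Appendix 1 keep patients who relapse or stop treatment in follow-up, and withdrawal is expected to be rare. SAP 6.4 leaves out only unscheduled assessments. Mixing relapse-triggered scores into visit means would itself distort them.

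Four further points carry weight. First, an arm difference can be unbiased under weaker conditions than an arm mean, for example if missingness depends on the month 4 score alike in both arms and the effect is additive. Second, SAP 10.2 calls even its modelled secondary outcomes exploratory, and a reader can form an unadjusted difference and interval from the reported n, mean and SD. Third, equal variances are doubtful for a cumulative score that should not decrease. In general the variance saved against the change score is (s₁ − ρs₂)², where s₁ and s₂ are the SDs at month 4 and follow-up. This is never negative, but it vanishes when s₂/s₁ = 1/ρ (1.11 at ρ = 0.9), so the CDA gain could be close to nil. Fourth, a normal model for a 0–64 damage count needs justification, and no model repairs the rule in SAP 9.8 that unticked items count as absent.

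These points limit the size of the concern. They do not supply the missing estimate. Exploratory results still need a stated method, and an interval built from the tables would be the less precise, unadjusted one.

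**Conclusion.** The point holds as a gap in prespecification and precision. In this SAP neither CDA nor SF-36 has a between-arm estimate or confidence interval, and the observed-case method does not in general match the missing-at-random assumption in SAP 8.5. Bias is a minor part: about 0.04 SD at most at the planned 5% drop-out, under an assumed mechanism confined to one arm. The precision loss is clearest for SF-36, at 25–49% of the variance against raw means if ρ is 0.5 to 0.7. Against change scores it is 15–25% at the same ρ, and less for CDA if its correlation is higher. All these percentages rest on assumed correlations and equal variances, which the documents do not give. The change is worth making because it uses data already collected, but it does not affect the primary analysis.

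**What to change.** - In SAP 12.2 and 9.8, prespecify one repeated-measures model each for PCS, MCS and CDA total on the full analysis population. Include arm, visit, arm by visit, month 4 score by visit and the three stratification factors.
- Report adjusted arm differences with 95% CI at months 24 and 36, labelled exploratory if wished. Both visits fall within every patient's minimum follow-up, unlike months 42 and 48.
- For CDA, add a check of the normal model, for example robust standard errors or a count model.
- In SAP 12, state that the SF-36 analysis is covered by this SAP.
- Keep the descriptive tables.

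The cost is SAP wording, modest programming and a modelling assumption for CDA. No new data are needed. Protocol 10.4 allows randomisation up to 14 days before month 4, so some month 4 questionnaires may be completed after the allocation is known. No maintenance drug is given before that visit, so the score remains a reasonable baseline, but the SAP should say so.

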## 8.6 Interim Analyses and Data Monitoring

(ICH E3; 9.7.1, 11.4.2.3. ICH E9; 4.1, FDA Feb 2010 “Guidance for Industry Adaptive Design Clinical Trials for Drugs and Biologics”)

No interim analyses are planned.

An independent Data Monitoring Committee (Data and Safety Monitoring Board, DSMB) will be convened to review efficacy and safety data on a quarterly basis, and will advise on the need for any additional analyses or alterations to the conduct or even continuation of the trial if there are major safety concerns.

## 8.8 Multi-centre Studies

(ICH E3; 9.7.1, 11.4.2.4. ICH E9; 3.2)

RITAZAREM is a joint venture of the European Vasculitis Study Group (EUVAS) and the Vasculitis Clinical Research Consortium (VCRC). RITAZAREM will occur in multiple centres internationally including Europe, North America and Australia/New Zealand. Plans are for approximately 50–60 centres to recruit patients.

Data is recorded in a single MACRO database across all study centres. Study centre will form part of the information recorded, so that it can be identified during the statistical analysis. Recruitment and patient's retention rate will be reported by site and grouped by country.

## 8.9 Multiple Testing

(ICH E3; 9.7.1, 11.4.2.5. ICH E9; 2.2.5)

For the primary outcome of the trial, the primary intention to treat analysis will be based on a Cox proportional hazard model. There will be a closed testing procedure, first the null hypothesis will be for a hazard ratio of 1 at all time points. If this is rejected at a 5% level then two further sub-hypotheses will be examined using time-varying covariates:

1. A hazard ratio of 1 up to 24 months post-randomisation (i.e. during treatment).
2. A hazard ratio of 1 after 24 months post-randomisation (i.e. post-treatment).

## 9 Summary of Study Data

All continuous variables will be summarised using the following descriptive statistics: n (non-missing sample size), mean, standard deviation, median, maximum and minimum. The frequency and percentages (based on the non-missing sample size) of observed levels will be reported for all categorical measures. Summary tables will be structured with a column for each treatment arm ("Azathioprine", "Rituximab"), as well as a total column. Additionally some summary tables (e.g. baseline demographic) will also be presented split by induction regimen ("1A", "1B"). All tables will be annotated with the total population size relevant to that table/treatment, including any missing observations. In general, where appropriate, data will be listed sorted by site, subject and visit.

Only deviations from the general overview will be noted in the subsequent sub-sections within section 9.

## 9.1 Subject Disposition

### 9.1.1 Visit dates

The three phases of the trial are defined as follows:

1. Induction phase: enrolment to Month 4 (inclusive)
2. Maintenance phase: Month 4 to Month 24 (inclusive)
3. Follow-up phase: Month 24 (exclusive) to Month 36/42/48 (common close)

A target randomisation date (*RandomDate*) four months in the future was generated at enrolment to help local sites organise rituximab or azathioprine supply for the maintenance phase. Patients could be randomised from 14 days before to 14 days after Month 4 visit. If patients attended their Month 3 visit and were in remission, then they could be randomised up to 14 days before Month 4. Those not in remission at Month 3 were reassessed at Month 4 and, if they entered remission, were then randomised and commenced allocated therapy within the next 14 days. Those not in remission at Month 4 were not randomised (even if they had been considered in remission at Month 3 visit) and treated at the investigator's discretion, follow-up data continued to be collected unless consent was withdrawn. **Maintenance therapy (with either treatment) was not administered before the Month 4 visit.** Consequently, the month 4 visit will be considered as both the end of the Induction Phase of the trial and the beginning of the Maintenance Phase of the trial. It will be used as time zero for the primary endpoint of the Maintenance Phase (time to disease relapse from randomisation).

When calculating time elapsed in days, months or years (e.g. when calculating time from randomisation), full dates (yyyy-mm-dd) appropriately formatted, will be converted to the number of days since 1970-01-01, with negative values for earlier dates, following the default representation of dates in the R language. A full year is taken to be 365.25 days long, a standardisation that approximates for the

---

 <https://stat.ethz.ch/R-manual/R-devel/library/base/html/Dates.html>

occurrence of leap years. A month is taken to be 1 / 12th of a full year. First day of the month/year will be used for fuzzy dates.

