#### 13.4.2 Assessment of causality

*Definitely:* A causal relationship is clinically/biologically certain. **This is therefore an Adverse Reaction**

*Probable:* A causal relationship is clinically / biologically highly plausible and there is a plausible time sequence between onset of the AE and administration of the investigational medicinal product and there is a reasonable response on withdrawal. **This is therefore an Adverse Reaction.**

*Possible:* A causal relationship is clinically / biologically plausible and there is a plausible time sequence between onset of the AE and administration of the investigational medicinal product. **This is therefore an Adverse Reaction.**

*Unlikely:* A causal relation is improbable and another documented cause of the AE is most plausible. **This is therefore an Adverse Event.**

*Unrelated:* A causal relationship can be definitely excluded and another documented cause of the AE is most plausible. **This is therefore an Adverse Event.**

Unlikely and Unrelated causalities are considered NOT to be trial drug related  
Definitely, Probable and Possible causalities are considered to be trial drug related

A pre-existing condition must not be recorded as an AE or reported as an SAE unless the condition worsens during the trial and meets the criteria for reporting as a SAE or selected adverse event (see section 13.3.)

Investigators will be prompted on the follow up form completed at each visit to complete an infection form or new malignancy form if either of these events have occurred since the last trial visit. Details regarding the changes in dose of IMPs (rituximab, azathioprine, methotrexate and mycophenolate mofetil) including new dose, date of change and reason for change will be captured on the follow up form.

The occurrence of hypogammaglobulinaemia (IgG < 5g/l) is flagged when data is entered into the trial database, and is reported to the DSMB on a 6 monthly basis.

The occurrence of a relevant laboratory abnormality or the addition of a new concomitant medication will be flagged as data is entered into the trial database. An adverse event form will be generated, and the relevant abnormality and data identified pre-filled on the form. Forms will then be sent to investigators for completion. Completed adverse event forms must be submitted to the CCTU within 2 weeks.

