### 1. Baseline Medical History

- **Prior disease duration (years)** – calculated from the date of diagnosis to the date of screening. First day of the month/year will be used for fuzzy dates. Date difference in years will be rounded to 1 decimal figure.
- **Historical ANCA positivity (Positive both/anti-PR3/anti-MPO, Negative, Missing)** – a categorical variable, calculated from variables in the Enrolment Form recording historical positivity to anti-PR3 and anti-MPO ANCA. Calculated according to the following rules (if only one value is confirmed and the other is missing, the missing one is assumed to be negative):

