## 11 Safety Analyses

### 11.1 Serious Adverse Events

All serious adverse events (SAE), including serious adverse drug reactions will be reported according to guidance in sections 13.4 and 13.5 of the protocol.

All Serious Adverse Events must be reported to the central trials co-ordinator or trial physician in Cambridge within 24 hours of the investigator becoming aware of the event and will be entered in a separate database. Individual SAEs will be assessed by the trial physician, and if advice is needed, this will be sought from one of the CIs, blinding them to treatment allocation. Monthly SAE listings, blinded to treatment allocation, will be reviewed by both CIs however. The Sponsor has to keep detailed records of all SAEs reported to them by the trial team.

Frequency tables for all SAEs will be reported using the safety population and stratified by both treatment arm and induction regimen as well as their interaction.

Separate tables will report:

- SAEs where date of onset occurred after randomisation
- SAEs occurring during treatment (up to 20 months after randomisation)

---

 SAEs occurring during the induction period (prior to randomisation) were reported separately, see Induction Phase SAP and report.

- SAEs occurring after treatment ended (from 20 months after randomisation onwards)

Additionally, counts of subjects and events stratified by relatedness (Unrelated/Related) will be reported, grouped by System Organ Class, High Level Group Term and Preferred Term based on the MedDRA code.

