## 11.2 Adverse Events

In addition to all SAEs, the following selected adverse events (AEs) are being collected as part of the RITAZAREM trial:

1. Infections (all episodes requiring treatment with intravenous (IV) or oral antibiotics or infections that are commonly understood to be opportunistic)
2. Occurrence of hypogammaglobulinemia (IgG <5g/l)
3. Occurrence of hypogammaglobulinemia (IgG <3g/l)
4. An adverse event that results in a change in dose of trial IMPs (rituximab, azathioprine, methotrexate or mycophenolate mofetil (MMF))
5. An adverse event that results in the addition of a relevant concomitant medication (see section 13.3.1 for list)
6. An adverse event manifested by the occurrence of a relevant laboratory abnormality (see section 13.3.2 for list)
7. New malignancies

Infections are recorded using the Infection Form and entered in the MACRO database. Frequency tables for serious and non-serious infections with date of onset occurring in the maintenance phase will be reported using the safety population and stratified by induction regime. The number of patients with newly occurring IgG < 5g/L and newly occurring IgG < 3g/L will be reported. Additionally, counts of subjects and events for non-serious infections will be reported, grouped by High Level Group Term and Preferred Term based on the MedDRA code.

Individual listings of infections are reported to the DSMB and reviewed quarterly.

New malignancies are recorded using the New Malignancy Form and entered in the MACRO database. All instances of new malignancies detected during the maintenance phase will be reported as individual listings sorted per patient by site. The following detail will be reported:

- Treatment arm
- Malignancy Detection date
- Malignancy Diagnosis date
- Malignancy Site
- Malignancy Type
- Malignancy Reoccurrence
- Malignancy Treatment (Surgery, Radiotherapy, Chemotherapy, Other)
- Malignancy Associated with SAE (Yes/No)
- Malignancy Comments

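### The first-of-month/year rule for partial dates has no exception for safety onset dates, so some post-randomisation SAEs and infections can be dated before the month 4 visit or moved across the 20-month cut

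*SAP*

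**What the plan says.** SAP 9.1.1 has a general paragraph on date arithmetic. It opens with "When calculating time elapsed in days, months or years (e.g. when calculating time from randomisation" as its example and ends with "First day of the month/year will be used for fuzzy dates". The rule is repeated in SAP 9.2, item 1, for prior disease duration, which is "calculated from the date of diagnosis to the date of screening. First day of the month/year will be used for fuzzy dates". The general statement in 9.1.1 is not limited to such historical dates.

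The same section fixes the boundary: "the month 4 visit will be considered as both the end of the Induction Phase of the trial and the beginning of the Maintenance Phase".

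The safety sections then classify events by date:

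- SAP 11.1 tabulates "SAEs where date of onset occurred after randomisation", then "SAEs occurring during treatment (up to 20 months after randomisation"), then those from 20 months onwards. A footnote says that induction-period SAEs were reported separately.
- SAP 11.2 plans "Frequency tables for serious and non-serious infections with date of onset occurring in the maintenance phase".

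Neither section has its own rule for a partial onset date, a floor at the month 4 visit, or a step to query such dates. On data capture, Protocol 13.4.2 says: "Investigators will be prompted on the follow up form completed at each visit to complete an infection form or new malignancy form". After month 4 those visits are 3 to 6 months apart (Protocol 12.3.1).

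**The concern.** Setting a partial date to the first day of its month or year always picks the earliest possible date. For a date of diagnosis years before entry this does little harm. For an onset date that is compared with the month 4 visit, it can change the table in which the event is counted.

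Take a hypothetical patient whose month 4 visit was on 10 March 2016. An infection on 20 March 2016, recorded only as March 2016, is dated 1 March and falls before randomisation. In the same patient the 20-month cut is about 9 November 2017. An SAE on 20 November 2017, recorded only as November 2017, is dated 1 November and counted as during treatment.

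At time zero the error has one direction: post-randomisation events can be moved out and none can be moved in. If the separate induction report was compiled before the event occurred, a displaced SAE may appear in neither report. The planned Kaplan-Meier plot of SAE-free survival (SAP 13) would receive a negative time for such an event, and the SAP does not say how to handle it. Long-term rituximab safety is a secondary objective and the infection rate is secondary endpoint 7.

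**Working it through.** The plan states no figure on this point, so there is none to reproduce. The check applies the SAP rule to hypothetical events.

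**Inputs from the SAP.** Rule: first day of the known month or year (9.1.1). Month = 365.25/12 = 30.44 days (9.1.1). Boundary: month 4 visit (9.1.1). Second cut: 20 months, or 608.75 days, later (11.1). Follow-up from the visit is 20 months to the end of treatment, 32 months to month 36 and 44 months to month 48, that is 608.75, 974 and 1,339.25 days.

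**Assumptions.** Month 4 visits are spread evenly over the calendar. The event rate is constant from the day after the visit. The month 4 visit stands for randomisation in the safety tables too. The share q of onset dates that lack only the day is not given, so a range of 1% to 20% is used.

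**1. Displacement at time zero.** For a calendar unit of L days with the visit on day d, the displaced events are those on the L − d remaining days of that unit, for d ≥ 2. The mean is (L − 1)(L − 2)/(2L).

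- Day missing, L = 30.44: 29.44 × 28.44/60.88 = 13.75 days. Ignoring whole-day effects gives L/2 = 15.2 days.
- Year only, L = 365.25: 364.25 × 363.25/730.5 = 181 days.

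Divided by the length of follow-up, as a share of partially dated events:

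| Follow-up | Day missing | Year only |
|---|---|---|
| 20 months | 13.75/608.75 = 2.3% | 181/608.75 = 29.8% |
| 32 months | 13.75/974 = 1.4% | 181/974 = 18.6% |
| 44 months | 13.75/1,339.25 = 1.0% | 181/1,339.25 = 13.5% |

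With 15.2 days, the 20-month day-missing figure is 2.5%. A simulation of 1,000,000 events gave 2.3%, 1.4% and 1.0% (day missing) and 29.8%, 18.7% and 13.5% (year only). It moved no pre-randomisation event to after randomisation. Day-missing losses are concentrated early: 13.75/30 to 15.2/30, or 46–51%, of day-missing events in the first 30 days.

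**2. Share of all post-randomisation events, day missing.** The lowest value is 1% × 1.0% = 0.01%. The highest is 20% × 2.5% = 0.5%.

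**3. The 20-month cut.** A partially dated event after the cut moves to during treatment if it shares the calendar unit of the cut. The mean is (L − 1)/2 days: 14.7 (day missing) or 182 (year only). Post-treatment follow-up is 12 months (365.25 days) to 24 months (730.5 days).

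- Day missing: 14.7/365.25 = 4.0% to 14.7/730.5 = 2.0%.
- Year only: 182/365.25 = 50% to 182/730.5 = 25%.

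**4. Infections under two definitions of the maintenance phase.** SAP 9.1.1 defines it as months 4 to 24. SAP 4.2 describes it as running from randomisation to month 48, and SAP 6.4 also includes follow-up in it.

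- Months 4 to 24, with 32 months of follow-up, as a share of all partially dated events: 1.4% lost at the start and 14.7/974 = 1.5% gained at the end (day missing). For year-only dates the simulation gives 18.7% lost and 18.7% gained. The net count hardly changes, although the wrong events are counted.
- To month 48: the losses in step 1 are not offset.

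**5. The opposite error.** Suppose every partial date compatible with post-randomisation onset were counted as post-randomisation. Then induction events that share the visit's month would be pulled in: over the 4 induction months (121 days), 14.7/121 = 12% of those with the day missing. For year-only dates the simulation gives 83%. A floor at the month 4 visit therefore needs a check against reporting information, and year-only dates should not be imputed without it.

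**The case against.** The strongest reply is that nothing shows the rule will affect any safety event. No section says that an SAE or infection onset date is partial. SAEs are reported within 24 hours of the investigator becoming aware, so missing days should be uncommon. Infection forms ask about events since the last visit, so an investigator should rarely be unable to name the month. The rule sits under visit dates, and the only variable to which the SAP explicitly applies it is date of diagnosis. All of this limits the size of the problem. It does not remove the gap, because 9.1.1 is worded generally, uses time from randomisation as its example, and no later section overrides it.

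Four stronger readings are tempting and are not supported:

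- **That the tables do lose events.** The documents support only that they can. Only events that share the calendar month or year of the visit are at risk.
- **That losses near 30% are to be expected.** That figure needs events during the trial for which only the year is known.
- **That rituximab safety is biased because the first maintenance infusion falls in the affected weeks.** The rule ignores arm, and control therapy also starts at month 4. Bias between arms would need different partial-date rates or different early event rates by arm, and neither is shown.
- **That the SAE tables are secondary endpoint 6.** That endpoint is worded as severe adverse events, and Protocol 13.1.3 distinguishes severe from serious.

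It is also fair to object that a floor at the month 4 visit alone would create the opposite error (step 5), and that induction SAEs already reported could be counted twice. The fix has to deal with both.

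**Conclusion.** The concern holds as a gap with a defined direction and a probably small size. As written, the SAP can date a post-randomisation SAE or infection before randomisation, and can move a post-treatment event into the treatment period, because a rule suited to historical dates is stated for all elapsed-time calculations.

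For day-missing dates the displacement at time zero is about 2.3–2.5% of partially dated events over 20 months, or roughly 0.01–0.5% of all post-randomisation events if 1–20% of dates lack the day. Only year-only dates could make it material, and they should be rare. For infections, whether there is a net loss depends on which definition of the maintenance phase applies.

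These figures rest on evenly spread visit dates, a constant event rate and an assumed range for q. The true number of partial onset dates is not in the documents. The change is worth making because the misclassification is avoidable at little cost, not because a distorted safety comparison has been shown.

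**What to change.** In SAP 9.1.1, restrict the first-day rule to historical dates such as date of diagnosis. For SAE, infection and malignancy onset, add the following:

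1. Query partial dates first. SAP 8.1 already routes data queries to data management.
2. If a date stays unresolved and only the day is missing, use the later of the first of the known month and the month 4 visit date, unless the report date, or the visit at which the event was first reported, places the event before the month 4 visit.
3. Apply the same logic at the 20-month cut.
4. Do not impute year-only dates without such bounding information.
5. Check displaced SAEs against the induction report, so that none is counted twice or omitted from both.
6. List all imputed onset dates and count them by arm. That count shows whether the issue matters.

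State in SAP 11.2 which definition of the maintenance phase selects the infections.

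The cost is a few lines of SAP text and code, plus the queries. The downside is that, without the report-date check in item 2, about 12% of day-missing induction events could be counted as post-randomisation.
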